8.3.2 DEFINITION OF SERIOUS ADVERSE EVENTS (SAE)

An adverse event (AE) or suspected adverse reaction is considered "serious" if, in the view of either the investigator or sponsor, it results in any of the following outcomes: death, a life-threatening adverse event, inpatient hospitalization or prolongation of existing hospitalization, a persistent or significant incapacity or substantial disruption of the ability to conduct normal life functions, or a congenital anomaly/birth defect. Important medical events that may not result in death, be life-threatening, or require hospitalization may be considered serious when, based upon appropriate medical judgment, they may jeopardize the participant and may require medical or surgical intervention to prevent one of the outcomes listed in this definition. Examples of such medical events include allergic bronchospasm requiring intensive treatment in an emergency room or at home, blood dyscrasias or convulsions that do not result in inpatient hospitalization, or the development of drug dependency or drug abuse.

8.3.3 CLASSIFICATION OF AN ADVERSE EVENT

8.3.3.1 SEVERITY OF EVENT

The CTCAE V. 4.03 will be used in this study. Each adverse event must be assigned a Grade, which refers to the severity of the adverse event. The CTCAE v4.03 displays Grades 1 through 5 with unique clinical descriptions of severity for each adverse event on this general guideline:

Grade 1 – Mild AE

Grade 2 – Moderate AE

Grade 3 – Severe AE

Grade 4 – Life-threatening or disabling AE

Grade 5 – Death related to AE

8.3.3.2 RELATIONSHIP TO STUDY INTERVENTION

All adverse events (AEs) must have their relationship to study intervention assessed by the clinician who examines and evaluates the participant based on temporal relationship and his/her clinical judgment. The degree of certainty about causality will be graded using the categories below. In a clinical trial, the study product must always be suspect.

- **Related** – The AE is known to occur with the study intervention, there is a reasonable possibility that the study intervention caused the AE, or there is a temporal relationship between the study intervention and event. Reasonable possibility means that there is evidence to suggest a causal relationship between the study intervention and the AE.
- **Not Related** – There is not a reasonable possibility that the administration of the study intervention caused the event, there is no temporal relationship between the study intervention and event onset, or an alternate etiology has been established.

OR

- **Definitely Related** – There is clear evidence to suggest a causal relationship, and other possible contributing factors can be ruled out. The clinical event, including an abnormal laboratory test result, occurs in a plausible time relationship to study intervention administration and cannot be explained by concurrent disease or other drugs or chemicals. The response to withdrawal of the study intervention (dechallenge) should be clinically plausible. The event must be pharmacologically or phenomenologically definitive, with use of a satisfactory rechallenge procedure if necessary.
- **Probably Related** – There is evidence to suggest a causal relationship, and the influence of other factors is unlikely. The clinical event, including an abnormal laboratory test result, occurs within a reasonable time after administration of the study intervention, is unlikely to be attributed to concurrent disease or other drugs or chemicals, and follows a clinically reasonable response on withdrawal (dechallenge). Rechallenge information is not required to fulfill this definition.
- **Potentially Related** – There is some evidence to suggest a causal relationship (e.g., the event occurred within a reasonable time after administration of the trial medication). However, other factors may have contributed to the event (e.g., the participant's clinical condition, other

concomitant events). Although an AE may rate only as “possibly related” soon after discovery, it can be flagged as requiring more information and later be upgraded to “probably related” or “definitely related”, as appropriate.

- **Unlikely to be related** – A clinical event, including an abnormal laboratory test result, whose temporal relationship to study intervention administration makes a causal relationship improbable (e.g., the event did not occur within a reasonable time after administration of the study intervention) and in which other drugs or chemicals or underlying disease provides plausible explanations (e.g., the participant’s clinical condition, other concomitant treatments).
- **Not Related** – The AE is completely independent of study intervention administration, and/or evidence exists that the event is definitely related to another etiology. There must be an alternative, definitive etiology documented by the clinician.

8.3.3.3 EXPECTEDNESS

The Investigator will be responsible for determining whether an adverse event (AE) is expected or unexpected. An AE will be considered unexpected if the nature, severity, or frequency of the event is not consistent with the risk information previously described for the study intervention.

8.3.4 TIME PERIOD AND FREQUENCY FOR EVENT ASSESSMENT AND FOLLOW-UP

The occurrence of an adverse event (AE) or serious adverse event (SAE) may come to the attention of study personnel during study visits and interviews of a study participant presenting for medical care, or upon review by a study monitor.

All AEs including local and systemic reactions not meeting the criteria for SAEs will be captured on the appropriate case report form (CRF). Information to be collected includes event description, time of onset, clinician’s assessment of severity, relationship to study product (assessed only by those with the training and authority to make a diagnosis), and time of resolution/stabilization of the event. All AEs occurring while on study must be documented appropriately regardless of relationship. All AEs will be followed to adequate resolution.

Any medical condition that is present at the time that the participant is screened will be considered as baseline and not reported as an AE. However, if the study participant’s condition deteriorates at any time during the study, it will be recorded as an AE.

Changes in the severity of an AE will be documented to allow an assessment of the duration of the event at each level of severity to be performed. AEs characterized as intermittent require documentation of onset and duration of each episode.

The Principal Investigator will record all reportable events with start dates occurring any time after informed consent is obtained until 7 (for non-serious AEs) or 30 days (for SAEs) after the last day of study participation. At each study visit, the investigator will inquire about the occurrence of AE/SAEs since the last visit. Events will be followed for outcome information until resolution or stabilization.

8.3.5 ADVERSE EVENT REPORTING

Serious adverse events will be collected throughout the study period. All serious adverse events must be reported to HiDO Technologies within 24 hours of discovery or notification of the event. Initial serious adverse event information and all amendments or additions must be recorded on a Serious Adverse Event Report Form and submitted to HiDO Technologies. The Principal Investigator will notify the IRB of serious adverse events within seven days or as otherwise specified by local policies.

Disease-related events (DREs) can be expected to occur among the study population, which may include HIV/AIDS patients. These events are recorded by research staff, but are not reported as for AEs.

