2.3 RISK/BENEFIT ASSESSMENT

2.3.1 KNOWN POTENTIAL RISKS

A potential risk to participants is breach of confidentiality, which exists both as an immediate and long-term risk. There is also an immediate risk that the platform hardware or software may malfunction in some way, which may affect data capture, data transmission, or medication dispensing. These errors may affect the reliability of the device in providing timely dosage reminders, accurate remote monitoring, and accurate dispensing of medication.

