7 STUDY INTERVENTION DISCONTINUATION AND PARTICIPANT DISCONTINUATION/WITHDRAWAL

7.1 DISCONTINUATION OF STUDY INTERVENTION

Discontinuation from HiDO platform use does not mean discontinuation from the study, and remaining study procedures should be completed as indicated by the study protocol. Although not expected to occur, if a clinically significant finding is identified after enrollment, the investigator or qualified designee will determine if any change in participant management is needed. Any new clinically relevant finding will be reported as an adverse event (AE).

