8.3 ADVERSE EVENTS AND SERIOUS ADVERSE EVENTS

8.3.1 DEFINITION OF ADVERSE EVENTS (AE)

Adverse event means any untoward medical occurrence associated with the use of an intervention in humans, whether or not considered intervention-related (21 CFR 312.32 (a)).

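### Section 8.3.5 exempts undefined disease-related events from AE reporting, in conflict with 7.1 and 8.3.4, so HIV worsening after a device failure could be recorded with no assessment of its link to the device

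*Combined protocol and SAP*

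**What the plan says.** Three places in the combined protocol and SAP govern how a clinical worsening is classified.

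- Section 8.3.5 (Adverse Event Reporting) sets up a separate class: "Disease-related events (DREs) can be expected to occur among the study population, which may include HIV/AIDS patients". It continues: "These events are recorded by research staff, but are not reported as for AEs". There is no list of qualifying events, and no exception for events that are serious or that follow a device malfunction. Section 10.3 only spells out the abbreviation.
- Section 8.3.4 treats conditions present at screening as baseline, but adds that if the participant's "condition deteriorates at any time during the study, it will be recorded as an AE".
- Section 7.1, on stopping use of the platform, says: "Any new clinically relevant finding will be reported as an adverse event (AE").

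Section 2.3.1 names hardware or software malfunction as a known risk, "which may affect data capture, data transmission, or medication dispensing". Section 2.2 describes what follows from poor ART adherence: loss of viral suppression, resistant virus, progression to AIDS, opportunistic infections and AIDS-related cancers.

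**The concern.** The device controls delivery of the treatment for the participants' underlying disease. If it fails to dispense or to remind, the plausible clinical harm is worsening of that disease. An HIV-related event is also what staff would most naturally call disease-related. The exemption in 8.3.5 therefore covers the kind of event through which a device failure would show itself clinically.

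At stake is whether someone is required to ask if the device contributed. A staff member following 7.1 or 8.3.4 would treat the event as an AE, and a colleague following 8.3.5 would not. Both would be complying with the protocol.

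**Working it through.** No arithmetic applies. The plan states no figure on this point and gives no event rate. The check takes one illustrative event through each rule: a non-serious HIV-related worsening that follows a period in which the device failed to dispense.

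1. **Definition (8.3.1).** An AE is "any untoward medical occurrence associated with the use of an intervention in humans, whether or not considered intervention-related". Disease-related events are not excluded, so the event qualifies.
2. **New findings (7.1).** If the worsening is a new finding of clinical relevance, it is to be *reported* as an AE. This section does not mention deterioration; it applies by the breadth of its wording.
3. **Deterioration (8.3.4).** Section 4.1 describes the participants as having HIV/AIDS, so HIV is a baseline condition and its worsening falls under the deterioration rule. It is to be *recorded* as an AE. The same section adds: "All AEs occurring while on study must be documented appropriately regardless of relationship".
4. **Disease-related events (8.3.5).** If staff label the event a DRE, it is recorded but not reported in the way AEs are.
5. **Precedence.** None is stated. Because DRE is undefined, the label is left to whoever records the event.

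What depends on the label:

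| Step | Section | Stated for AEs | Stated for DREs |
|---|---|---|---|
| Severity grade | 8.3.3.1 | yes | no |
| Relationship to the device | 8.3.3.2 | yes | no |
| Expectedness | 8.3.3.3 | yes | no |
| Follow-up to resolution | 8.3.4 | yes | no |
| Recording by staff | 8.3.4, 8.3.5 | yes | yes |

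The relationship rule reads "All adverse events (AEs) must have their relationship to study intervention assessed by the clinician". It says nothing of events outside the AE class.

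Other routes that might catch the event:

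- **SAE route.** Section 8.3.5 requires notification of the sponsor within 24 hours and of the IRB within seven days. Section 8.3.2 defines a serious event as a kind of AE or suspected adverse reaction, and 8.3.5 does not say whether a serious DRE counts. A non-serious event is outside this route.
- **Unanticipated problem (8.4.1, 8.4.2).** This route can cover non-serious events, but the event must be both unexpected and at least possibly related to the research. Section 8.3.5 describes DREs as events that can be expected, and no relationship judgement is required for them.
- **Unanticipated adverse device effect (8.3.6, 8.4.1).** This route covers serious effects not previously identified. Section 2.3.1 lists malfunction but no clinical outcome of it, so a serious worsening caused by malfunction could qualify. A non-serious one would not.
- **Log audit (8.2).** The audits examine dosing and could reveal falling adherence. They do not examine clinical events.
- **Later review.** Safety analyses (9.4.4) and safety oversight (10.1.6) are both marked as not applicable. The schedule in 1.3 lists no viral load or CD4 measurement.

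**The case against.** The strongest reply separates recording from reporting. On that reading a DRE is recorded as an AE under 8.3.4, with the assessments that follow, and 8.3.5 merely spares it the onward reporting chain. Sections 8.3.4 and 8.3.5 would then agree. This is a possible reading and would close most of the gap. But the protocol does not state it: 8.3.5 says that staff record DREs, not that they record them as AEs. It also leaves 7.1, which does say reported, unreconciled.

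It can also be said that a disease-related category is an ordinary device, that serious events have other routes, and that the log audits look at the upstream mechanism. The point about serious events largely stands, subject to the silence on serious DREs. The audits are a real safeguard against unnoticed non-adherence, but they do not link a clinical event to it. A disease-related category is easier to defend when the product is unrelated to the disease; here it delivers the disease's treatment.

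A reader might go further and infer that this harm disappears from the record and from every reporting chain. The documents do not support that. DREs are still recorded, and the SAE, unanticipated-problem and device-effect routes remain.

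**Conclusion.** The inconsistency is real and worth correcting. The same worsening is an AE under 7.1 and 8.3.4 and may be outside AE reporting under 8.3.5, with no definition or precedence to settle it. The practical consequence is limited: an HIV-related event after a malfunction, most clearly a non-serious one, could be recorded without a severity grade, an expectedness judgement or an assessment of relationship to the device. For serious events the gap is one of ambiguity, not demonstrated omission.

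This rests on two assumptions: that staff would label HIV worsening disease-related, and that they would read 8.3.5 as an exemption from AE handling and not only from onward transmission.

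A reader might also infer that the trial's planned safety result would be biased towards finding no device-related events. The plan contains no such result, because 9.4.4 plans no safety analysis. Nor can the effect be sized by treating one event as a fraction of the 24 participants: that fraction is the same for any event in a study of this size and says nothing about how often the exemption would apply. Such events may be rare over 90 days.

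**What to change.** Make the following changes to classification and reporting. None of them touches clinical management.

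1. Reconcile 7.1, 8.3.4 and 8.3.5, and state which rule governs when more than one applies.
2. Define DRE, preferably with a list of qualifying events.
3. State in 8.3.5 that a serious DRE follows the SAE route.
4. Require every DRE to be assessed for relationship to the device, using the dose log and any record of malfunction for the preceding period. Handle any event judged possibly related as an AE.
5. Replace the not-applicable entry in 9.4.4 with a short descriptive summary that lists DREs beside AEs.

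The cost is some rewording, one assessment per DRE and a brief tabulation. Staff already record the events and the device already keeps dose logs. The protocol does not describe a separate malfunction log, so the sponsor should say where malfunctions are documented. The summary would be a new output, since no safety table is currently planned.

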8.3.6 SERIOUS ADVERSE EVENT REPORTING

The study investigator shall complete an Unanticipated Adverse Device Effect Form and submit to the reviewing Institutional Review Board (IRB) as soon as possible, but in no event later than 10 working days after the investigator first learns of the effect. The study sponsor is responsible for conducting an evaluation of an unanticipated adverse device effect and shall report the results of such evaluation to the reviewing IRB and participating investigators within 10 working days after the sponsor first receives notice of the effect. Thereafter, the sponsor shall submit such additional reports concerning the effect as FDA requests.

8.3.7 REPORTING EVENTS TO PARTICIPANTS

Not applicable.

8.3.8 EVENTS OF SPECIAL INTEREST

Not applicable.

8.3.9 REPORTING OF PREGNANCY

Not applicable.

8.4 UNANTICIPATED PROBLEMS

8.4.1 DEFINITION OF UNANTICIPATED PROBLEMS (UP)

The Office for Human Research Protections (OHRP) considers unanticipated problems involving risks to participants or others to include, in general, any incident, experience, or outcome that meets all of the following criteria:

- Unexpected in terms of nature, severity, or frequency given (a) the research procedures that are described in the protocol-related documents, such as the Institutional Review Board (IRB)-

approved research protocol and informed consent document; and (b) the characteristics of the participant population being studied;

- Related or possibly related to participation in the research (“possibly related” means there is a reasonable possibility that the incident, experience, or outcome may have been caused by the procedures involved in the research); and
- Suggests that the research places participants or others at a greater risk of harm (including physical, psychological, economic, or social harm) than was previously known or recognized.

This definition could include an unanticipated adverse device effect, any serious adverse effect on health or safety or any life-threatening problem or death caused by, or associated with, a device, if that effect, problem, or death was not previously identified in nature, severity, or degree of incidence in the investigational plan or application (including a supplementary plan or application), or any other unanticipated serious problem associated with a device that relates to the rights, safety, or welfare of participants (21 CFR 812.3(s)).

8.4.2 UNANTICIPATED PROBLEM REPORTING

The investigator will report unanticipated problems (UPs) to the reviewing Institutional Review Board (IRB) and to the Data Coordinating Center (DCC)/lead principal investigator (PI). The UP report will include the following information:

- Protocol identifying information: protocol title and number, PI’s name, and the IRB project number;
- A detailed description of the event, incident, experience, or outcome;
- An explanation of the basis for determining that the event, incident, experience, or outcome represents an UP;
- A description of any changes to the protocol or other corrective actions that have been taken or are proposed in response to the UP.

To satisfy the requirement for prompt reporting, UPs will be reported using the following timeline:

- UPs that are serious adverse events (SAEs) will be reported to the IRB within seven days of the investigator becoming aware of the event.
- Any other UP will be reported to the IRB within 30 days of the investigator becoming aware of the problem.

An investigator shall submit to the reviewing Institutional Review Board (IRB) a report of any unanticipated adverse device effect occurring during an investigation as soon as possible, but in no event later than 10 working days after the investigator first learns of the effect.

8.4.3 REPORTING UNANTICIPATED PROBLEMS TO PARTICIPANTS

Participants will be verbally notified about UPs as required to disclosure known risks and maintain informed consent.

Secondary endpoint (4) will be analyzed once all participants have completed the post-intervention interview.

9.2 SAMPLE SIZE DETERMINATION

TARGET SAMPLE SIZE: 24

The current study is a pilot study, the intent of which is to gather preliminary data on device usage to determine whether further study with a larger sample is both possible and merited based on early findings of the device's efficacy and usability. For this study, the expected effect of the device upon medication adherence is expected to be moderate to large, based on an expected 95% adherence rate post-study in relation to reported adherence rates in clinical trials of 54% to 68%, which is used to estimate baseline adherence.⁹ Based on the expectation of moderate treatment effect, a sample size of between 10-15 is indicated as sufficient.^{26,27} A target sample size of 24 should be sufficient to ensure at least 15 participants will complete the study at an estimated 60% completion rate of recruited participants.

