4.2 SCIENTIFIC RATIONALE FOR STUDY DESIGN

Our main goal is to demonstrate $\geq 95\%$ adherence to ART in all patients across 90 days. Admittedly, this is a very high bar. However, we are confident that we will achieve it, even for patients who have problematic use. Our informal user testing to date has shown remarkable adherence rates with the HiDO device, and these have improved as we have moved into the current version (Version 3).

For participants who completely withdraw from the study before 90 days, adherence percentage will only be calculated for the time that they participated. While we will likely glean important information from those who do drop out early, these dropouts will not affect our primary endpoint calculation. We may also fail to recruit a pool of participants that reflects the diversity of the national HIV patient population. We expect, however, to be close, and will be able to recruit a sample sufficient to intelligently plan for larger scale future testing in diverse populations. If successful, we will have demonstrated that our automated medication adherence platform is highly usable, preliminarily enables strict adherence to ART, and is ready for larger scale testing in Phase II.

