5.5 STRATEGIES FOR RECRUITMENT AND RETENTION

The target sample will approximate the distribution of HIV/AIDS patients by race and ethnicity, and will equally enroll men and women, as seen in Figure 3.

Figure 3. Target sample by gender, race, and ethnicity.

| Racial Categories | Ethnic Categories | | | | Total | |
|--|------------------------|----------|--------------------|----------|-----------|--|
| | Not Hispanic or Latino | | Hispanic or Latino | | | |
| | Female | Male | Female | Male | | |
| American Indian/ Alaska Native | 0 | 0 | 0 | 0 | 0 | |
| Asian | 0 | 0 | 0 | 0 | 0 | |
| Native Hawaiian or Other Pacific Islander | 0 | 0 | 0 | 0 | 0 | |
| Black or African American | 5 | 5 | 0 | 0 | 10 | |
| White | 4 | 4 | 3 | 3 | 14 | |
| More than One Race | 0 | 0 | 0 | 0 | 0 | |
| Total | 9 | 9 | 3 | 3 | 24 | |

Participants will be recruited from the outpatient population of HIV/AIDS patients in the San Francisco Bay region of California; the study will not enroll participants outside of the United States. Potential participants will be recruited using a 1-page flyer that will be posted in one or more medical practices in the Bay Area that specialize in the prevention and treatment of HIV/AIDS; providers and staff of these practices are not otherwise affiliated with the study.

It is expected that approximately 75% of screened patients will be determined eligible for study enrollment, so approximately 32 individuals will be screened to reach the target sample size (n=24), which we expect to occur at a rate of approximately 2 participants per week.

To aid retention efforts, medication adherence for each participant is monitored through the HiDO platform. The HiDO unit is first and foremost a medication adherence device. The device will transmit real time data about adherence and trial participation. To maintain study integrity, we cannot intervene to promote adherence beyond the reminders and prompts provided by the medication adherence system. That said, having the device in the home is a powerful, indirect participant retention tool.

To compensate participants for their time, participants will receive \$100 gift card, which is disbursed upon return of the HiDO device. Participants who do not complete study receive \$5 for each full week

from device setup to date of notification by either party of study withdrawal, delivered by Visa gift card at device pickup.

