7.2 PARTICIPANT DISCONTINUATION/WITHDRAWAL FROM THE STUDY

Participants are free to withdraw from participation in the study at any time upon request.

An investigator may discontinue or withdraw a participant from the study for the following reasons:

- Significant study intervention non-compliance
- If any clinical adverse event (AE), laboratory abnormality, or other medical condition or situation occurs such that continued participation in the study would not be in the best interest of the participant
- Disease progression which requires discontinuation of the study intervention
- If the participant meets an exclusion criterion (either newly developed or not previously recognized) that precludes further study participation
- Incarceration

The reason for participant discontinuation or withdrawal from the study will be recorded on the relevant Case Report Form (CRF). Participants who sign the informed consent form, and receive the study intervention, and subsequently withdraw, or are withdrawn or discontinued from the study, will be replaced as needed to ensure a sample size of at least 15 participants.

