9.3 POPULATIONS FOR ANALYSES

- Modified Intention-to-Treat Analysis Dataset: participants who are enrolled for at least 7 days of the 90-day intervention period
- Per-Protocol Analysis Dataset: participants who complete the 90-day intervention period and post-study interview and questionnaire.

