9.4.2 ANALYSIS OF THE PRIMARY EFFICACY ENDPOINT(S)

Given the small sample size and specification of secondary endpoints, descriptive statistics are sufficient to either accept or reject the null hypothesis.

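### Section 9.2: 24 recruited at the stated 60% completion rate gives 14.4 expected completers, so 24 alone does not ensure 15; minor, fixed by rewording 9.2 and clarifying 7.2

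*Combined protocol and SAP*

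**What the plan says.** Section 9.2 describes a pilot study and, citing two references, states that "a sample size of between 10-15 is indicated as sufficient". It then sets the recruitment target: "A target sample size of 24 should be sufficient to ensure at least 15 participants will complete the study at an estimated 60% completion rate". The rate applies to recruited participants and is given without a source. Section 9.2 does not refer to replacement.

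Section 7.2 has a replacement rule. Participants who consent, receive the intervention and then withdraw or are withdrawn "will be replaced as needed to ensure a sample size of at least 15 participants". It does not say whether those 15 are enrolled participants or completers. Section 4.4 defines completing the study as finishing all phases, including the last scheduled procedure, but 7.2 does not use that term.

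Four other places bear on how much the number matters:

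- Section 9.4.2 plans no inferential test of the primary endpoint: "descriptive statistics are sufficient to either accept or reject the null hypothesis". Section 9.4.3 says the same of the secondary endpoints.
- Section 4.2 keeps early withdrawals in the adherence calculation: "adherence percentage will only be calculated for the time that they participated".
- Section 7.1 still asks for the remaining procedures from people who stop using the device: "Discontinuation from HiDO platform use does not mean discontinuation from the study, and remaining study procedures should be completed".
- Section 9.3 limits the per-protocol set to "participants who complete the 90-day intervention period and post-study interview and questionnaire".

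**The concern.** The sentence in 9.2 carries both its inputs (24 and 60%) and its result (at least 15), and the result does not follow. It is off in two ways. The expected number of completers is below 15. In addition, an expected value near 15 would not ensure 15, because the number who complete varies by chance.

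This is the only place where the plan explains why the target is 24. A pilot that ran exactly to its planned completion rate would appear to miss its own stated figure. The silence on replacement also leaves it unclear whether enrolment may go past 24, and when staff should replace someone who withdraws.

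**Working it through.** **Inputs**

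- Recruited: 24 (9.2).
- Completion rate: 60% (9.2).
- Completers claimed: at least 15 (9.2).
- Range called sufficient: 10 to 15 (9.2).
- Not in the plan, assumed here: participants complete independently of one another, and a range of 55% to 65% around the unsourced 60%.

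**1. Reproducing the plan's figure**

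- Recruits needed for an expected 15: 15 / 0.60 = 25, against the stated 24. The plan's figure is reproduced to within one recruit, but not exactly.
- Expected completers from 24: 24 × 0.60 = 14.4, which is 0.6 short of 15.
- Completion rate at which 24 gives an expected 15: 15 / 24 = 62.5%.

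**2. Chance of reaching 15 without replacement**

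With X, the number of completers, distributed Binomial(24, p):

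| Completion rate p | Expected completers (24p) | P(X ≥ 15) | P(X ≥ 10) |
|---|---|---|---|
| 55% (assumed) | 13.2 | 0.299 | 0.935 |
| 60% (stated) | 14.4 | 0.489 | 0.978 |
| 65% (assumed) | 15.6 | 0.687 | 0.995 |

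Correcting the one-recruit gap does not rescue the word *ensure*: with 25 recruited at 60%, P(X ≥ 15) = 0.586. A 90% chance of at least 15 needs either 24 recruited with about 72% completion, or 30 recruited at 60% (0.903).

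**3. With replacement, if the 15 in Section 7.2 are completers**

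Enrol 24, then continue until 15 complete. Let N be the number enrolled when the 15th completer is reached (negative binomial, with replacements completing at the same rate). Total enrolment is max(24, N). Its mean is 27.8 at 55%, 26.1 at 60% and 25.0 at 65%. At the stated rate, the floor of 15 therefore costs about two enrolments beyond 24 on average.

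**The case against.** There is a fair case that little is wrong here.

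**The gap is the size of a rounding slip.** It is 0.6 of a participant, or one recruit, and the sentence is hedged by calling the rate an estimate. The exact rate for 15 of 24 is 62.5%, which a planner might loosely call 60%. This stands as a reason for low weight. It does not make the sentence right: 14.4 does not round to 15, and even at 62.5% the chance of at least 15 is only about 59%.

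**Section 7.2 may already secure the 15.** It uses the same number and the same verb as 9.2, in a clause about withdrawals, so the natural reading is that both sections mean the same floor. A reader might instead take its 15 as enrolled participants and infer that replacement would never be triggered. That reading is strained, since with 24 enrolled it would leave the clause with almost nothing to do. What stands is that 7.2 does not say completers, and that 9.2 credits the 15 to 24 and 60% alone.

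**Nothing downstream depends on 15.** This also stands. About 14 completers is inside the sufficient range, the analyses are descriptive, early withdrawals still contribute adherence data, and people who stop using the device are still asked for the interview. Only the per-protocol set needs both 90 days and the interview.

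**Conclusion.** The sentence in 9.2 is wrong as written, and the effect is minor. At the stated rate, 24 recruited gives 14.4 expected completers and, without replacement, about a 49% chance of at least 15 (30% to 69% over the assumed 55% to 65%). The lower end of the plan's own sufficient range, 10 completers, is reached with about 98% probability (94% to 99%). These probabilities assume independent completion. The expected value of 14.4 does not depend on that assumption.

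The documents do not support three stronger conclusions that a reader might draw:

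- *The study is too small, or the target must rise.* Section 9.2 calls 10 to 15 sufficient, and no test or power calculation rests on 15.
- *The trial has an even chance of failing.* The 49% applies only without replacement, and it is the chance of reaching a planning number, not of a usable result.
- *The screening figure in 5.5 is wrong.* That section says "approximately 32 individuals will be screened to reach the target sample size (n=24", which is a statement about reaching 24 and is itself approximate. It needs no edit.

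**What to change.** Restate the 9.2 sentence along these lines: *With 24 enrolled and an estimated 60% completion rate, about 14 completers are expected without replacement, within the 10-15 considered sufficient; withdrawn participants will be replaced under Section 7.2 as needed to reach at least 15 completers.*

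In 7.2, say *at least 15 completers*, and note that total enrolment may then exceed 24 (about 26 on average at 60% completion).

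If the sponsor does not intend the 15 in 7.2 to be completers, end the new 9.2 sentence at *considered sufficient*, so that the assurance of 15 is dropped there. The floor should not be removed from 9.2 until that has been settled, because 7.2 would still carry it.

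The cost is one sentence in 9.2 and a short clarification in 7.2. The target of 24, Section 5.5, the procedures and the analyses are unchanged.
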